4.6.3.1 Selected Adverse Events

Infection

Infections will be defined from the adverse event data using the MedDRA SOC of “Infections and Infestations.” During Primary CSR, adverse events that are reported as an infection by the investigator will also be included.

During Primary CSR, an infection has been defined as serious if the event is a serious adverse event or if the non-serious infection was treated with an IV anti-infective. For subsequent reporting, an infection has been defined as serious if the event is a serious adverse event.

The number of infections and serious infections per 100 patient-years will be calculated and summarized separately. The ninety-five percent CI of the incidence rates will be calculated using exact method based on Poisson distribution.

Summary of infections will be presented by SOC and PT, severity, and Dose. Similar summary tables will be also produced by serious infections.

Summary tables of infections and serious infections by pathogen information codes as well as listing of infections/serious infections with pathogen codes will be produced.

Infusion-Related Reactions

An IRR and its corresponding symptoms are collected on the dedicated eCRF.

The symptom(s) of an IRR and the IRR itself may be of different intensities. As other symptoms can be recorded as free-text on the eCRF page, symptoms will be coded in the MedDRA and summarized by PTs.

IRRs are categorized by the time of the event occurring (1) during the infusion, (2) after completion of the infusion while patient is in the clinic, and (3) within 24 hours of completion of the infusion and patient is not in the clinic. The number and percentage of patients with at least one IRR will be presented by infusion (patients with multiple events within an infusion will count only once). In addition, the total number of IRRs will be

summarized (multiple events will be counted). The total and percentage (based on the total number of patients with at least one IRR) will be summarized by most extreme intensity.

IRRs will be summarized by intensity and by infusion. For multiple events within a patient, the most extreme intensity will be taken.

Symptoms of IRR and symptoms of serious IRR will also be presented by infusion. This analysis will be produced for both the controlled treatment period and the OLE period.

The number of patients with at least one IRR, the total number of IRRs, and the number of IRRs will be summarized by the time of events.

Pregnancies

Any pregnancies that occur during the study will be listed.

4.6.4 Magnetic Resonance Imaging Data

Non-MS pathology that is reported by the local safety radiologist will be listed by treatment group.

4.6.5 Laboratory Data

General laboratory evaluation

All laboratory assessments will be summarized or listed when applicable.

Absolute value and change from baseline values at each visit will be summarized. The baseline value will be the last value prior to the first dose of study medication. When laboratory data are presented over time, these laboratory values will be time-windowed into a common visit structure. If multiple values of the same laboratory parameter occur within the same time window, the worst value for that parameter will be presented in the summary table.

A summary of the number and percentage of patients with abnormal laboratory outcomes will be produced by treatment group for each parameter.

In addition, for the liver laboratory parameters, the number and percentage of patients with an elevated post-baseline AST or ALT level during the 96-week controlled treatment period will be summarized by treatment.

CD19

The median CD19 cell count will be displayed graphically over time from the first infusion of study medication. The absolute CD19 count and change from baseline in the CD19 count will be summarized over time. At each timepoint, the number and percentage of patients whose CD19 counts have repleted will be presented. Repletion is defined as the CD19 count having returned to their baseline value or lower limit of normal (≥ 80 cells/ μ L), whichever is lowest.

Immunoglobulins

The mean immunoglobulin levels (IgG, IgM, and total Ig) will be displayed graphically over time from the first infusion of study medication. The absolute values and change from baseline will be summarized over time. At each timepoint, the number and percentage of patients with immunoglobulin levels lower than the lower limit of normal will be presented.

Anti-Drug Antibodies

Anti-drug antibodies (ADAs), also called human anti-human antibodies (HAHAs), will be summarized over the 96-week controlled treatment period by treatment group. The baseline prevalence and post-baseline incidence of ADAs will be displayed. The number of patients with treatment-induced ADA will also be displayed. A table will be presented that summarizes ocrelizumab serum concentrations ($\mu\text{g/mL}$) at timepoints where ADA samples were collected and analyzed. A listing by treatment of anti-ocrelizumab antibody data will be presented for patients with at least one ADA sampled datum.

Antibody Titers

If data are available, antibody titers for mumps, rubella, varicella, and *Streptococcus pneumoniae* will be summarized for number and percentages of patients with positive level.

For Mumps, an assay method was updated due to bacterial contamination in tubes. And, results from both the assay methods, Diamedix Elisa and Diasorin Liaison XL to be presented for OLE Phase.

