Duration: the OLE phase will continue as per local regulation or should the Sponsor decide to terminate the ocrelizumab program for MS. Unless terminated earlier for any of the reasons mentioned above, all participants may continue their treatment with open-label ocrelizumab as per the protocol until 31 December 2022. All participants must discontinue open-label ocrelizumab treatment within this study before 31 December 2022. *However, participants will be offered continuation of ocrelizumab treatment or a safety follow-up period via a rollover study (MN43964, OLERO).*

Participants who start treatment with commercial ocrelizumab or another disease-modifying therapy (DMT) will discontinue from the study completely and will not enter the safety follow-up period.

Treatment: during the OLE phase, all participants will receive the ocrelizumab 600-mg dosing regimen every 24 weeks.

Withdrawal: participants who withdraw from the OLE phase will be entered into the safety follow-up period.

Safety Follow-Up

Participants who discontinue treatment prematurely for any reason during the following periods will be entered into the safety follow-up period:

- Before completion of the 96-week double-blind, double-dummy, treatment period
- During the OLE phase screening period
- During the OLE phase
- Participants who choose not to enter the OLE phase or are not eligible for the OLE phase after completing the 96-week, double-blind, double-dummy, treatment period

In the OLE phase screening period, in the case of a participant who initially declines participation in the OLE phase and subsequently reconsiders the decision, the participant will have up to 24 weeks after the Week 96 visit to enter the OLE phase. In this instance, he or she should not have taken any prohibited medication.

The safety follow-up period will last for 48 weeks starting from the date of the last infusion of ocrelizumab/ocrelizumab placebo. Safety follow-up visits will be performed at 12-week intervals starting from the date of the participant's last visit (the withdrawal from Treatment Visit).

Because this study will be closed on 31 December 2022, participants already in safety follow-up may complete this study period in the rollover Study MN43964.

Participants who start treatment with commercial ocrelizumab or another DMT will discontinue participation in the study completely and will not enter or continue in the safety follow-up period.

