- ^a Safety follow-up will be carried out for 48 weeks starting from the date of last infusion of ocrelizumab. Visits will be performed at 12-week intervals starting from the date of the participant's Withdrawal from Treatment Visit. *As this study will be closed on 31 December 2022 participants already in safety follow-up may complete this study period in the rollover Study MN43964.* Safety follow-up applies to study participants who have completed the blinded treatment period (or open-label treatment period, if applicable) and to participants who withdraw early from treatment. The last scheduled safety follow-up visit will become the End of Observation visit and the participant will have completed the study. *Participants who start treatment with commercial ocrelizumab or another DMT will discontinue from the study completely and will not enter or continue in the safety follow-up period. A Withdrawal from Study visit will be performed at the time of study closure for participants not rolling over to Study MN43964.*
- ^b **Routine safety laboratory examination:** hematology, chemistry and urinalysis.
- ^c **FACS** including CD19 and other circulating B-cell subsets, T cells, natural killer cells and other leukocytes.
- ^d **HAHA and ocrelizumab drug concentration samples:** in case of anaphylaxis, anaphylactoid reaction, or serious or severe hypersensitivity reaction, HAHA and ocrelizumab concentration samples should be collected as close as possible to the event and then at 4 and 16 weeks postdose.
- ^e **Hepatitis monitoring:** hepatitis to be monitored only in participants with screening results of HBsAg-negative, HBcAb-positive and HBV DNA negative, inclusive.
- ^f Needs to be assessed only every 24 weeks.
- ^g **Protein biomarker sampling:** 6 mL blood sample in a plain tube without EDTA for serum isolation will be collected from all participants for analysis of protein biomarkers.
- ^h **MRI** should only be performed for participants who begin an alternative treatment for MS, within the time window of one month prior to the start of an alternative MS treatment (unless MRI has already been performed within prior 8 weeks).
- ⁱ A structured **telephone interview** will be performed by site personnel every 4 weeks (± 3 days) between visits until 48 weeks after the last infusion to identify and collect information on any changes in the participant's health status that warrant an unscheduled visit (including new or worsening neurological symptoms).

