4.1.6.8 Rationale for the Safety Follow-Up Period

Data collected during this period will allow for evaluation of B-cell repletion after stopping anti-CD20 treatment and allow collection of safety and efficacy data to document maintenance of the effect and/or the potential for a withdrawal effect.

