virus-associated infections, mostly mild to moderate, were also reported more frequently with ocrelizumab (approximately 5%–6%, simplex and zoster) than with comparators (approximately 3%).

During the controlled period of the pivotal trials, the proportion of participants with serious infections in RMS was lower in the ocrelizumab group (1.3%) than in the IFN β -1-a group (2.9%); in PPMS, the proportion of participants with serious infections was similar in both groups: 6.7% in the placebo group compared with 6.2% in the ocrelizumab group.

Serious opportunistic and fatal infections have occurred in participants with lupus and RA treated with ocrelizumab in Phase III clinical trials. Data from completed studies regarding infection risks with ocrelizumab treatment in these participant populations are provided in the Ocrelizumab IB.

No opportunistic infections were reported for any participant with MS treated with ocrelizumab during the controlled period of the pivotal trials.

In interventional clinical studies, there were no reports of hepatitis B reactivation in participants with MS treated with ocrelizumab, but it had been reported for 1 participant with RA treated with ocrelizumab. Hepatitis B virus screening should be performed in all participants before initiation of treatment with ocrelizumab as per local guidelines. Participants with active HBV should not be treated with ocrelizumab. Participants with positive serology should consult liver disease experts before start of treatment and should be monitored and managed following local medical standards to prevent hepatitis B reactivation. Ocrelizumab administration should be delayed for participants with active infection until the infection is resolved.

For PML, see Section [7.3.1.2](#).

Delayed Return of Peripheral B Cells

Treatment with ocrelizumab leads to rapid depletion of CD19+ B cells in blood by 14 days post-treatment (first timepoint of assessment) and is an expected pharmacologic effect. This was sustained throughout the treatment period. The longest follow-up time after the last ocrelizumab infusion is from 51 participants in Study WA21493 and indicates that the median time to B-cell repletion (returned to baseline or LLN, whichever occurred first) of B cells was 72 weeks (range: 27–175 weeks).

Decrease in Immunoglobulins

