4.6.9 OLE Period

All data collected after the first dose of OLE ocrelizumab will be presented by the actual treatment received during the DB period, including all SFU and B-cell monitoring data for patients who withdraw during the OLE. Some of the analyses performed for the double-blind treatment period will be repeated and updated for the safety endpoints collected during the OLE period. In general, AE, SAE profile, infections, serious infections, IRRs, conmeds and laboratory analysis such as CD19, Immunoglobulins will be presented.

Analyses pooling all safety data from the first dose of ocrelizumab (double blind and OLE periods) across multiple MS trials are described separately in a Global Safety Pooling SAP.

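### The planned by-timepoint percentage of patients with repleted B cells has no last-infusion origin, denominator or censoring rule, so it does not estimate recovery after stopping ocrelizumab

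*SAP*

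**What the plan says.** Protocol 4.1.6.8 gives several reasons for the safety follow-up (SFU). One is repletion: "Data collected during this period will allow for evaluation of B-cell repletion after stopping anti-CD20 treatment". The Synopsis sets its length: "The safety follow-up period will last for 48 weeks starting from the date of the last infusion of ocrelizumab/ocrelizumab placebo". Section 4.1.5 makes this up to 48 weeks. Visits with cell counts run every 12 weeks, but Table 2 footnote a counts them from the Withdrawal from Treatment Visit, not from the last infusion.

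Protocol 7.3.1.1 reports Phase II experience: "The longest follow-up time after the last ocrelizumab infusion is from 51 participants in Study WA21493", and there "the median time to B-cell repletion (returned to baseline or LLN, whichever occurred first) of B cells was 72 weeks (range: 27–175 weeks".

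The amendment rationale at the front of the protocol records that continued B-cell monitoring of participants not repleted at the end of SFU has been removed. The stated reason is that no increased safety risk was seen after stopping.

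SAP 4.6.5 defines repletion as a return to baseline or the lower limit of normal, whichever is lower. It then plans: "At each timepoint, the number and percentage of patients whose CD19 counts have repleted will be presented". Laboratory values shown over time are windowed into a common visit structure whose anchor is not stated. SAP 4.6.9 lists CD19 among the open-label outputs, "including all SFU and B-cell monitoring data for patients who withdraw during the OLE". SAP 4.6.8 likewise puts SFU data into the double-blind outputs. SAP 4.6.3 expects the time assigned to a patient's last Dose to reach 72 weeks or longer. SAP 4.7 says missing-data methods are given section by section; the CD19 text gives none.

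**The concern.** Recovery after stopping is a question about time since the last infusion. A percentage at each timepoint answers it only if the timepoint is measured from that infusion, the denominator is fixed or corrected for loss, and those who leave are handled explicitly. None of this is specified.

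Three features make the gap matter.

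- Period outputs that combine on-treatment and off-treatment samples mix participants who cannot have repleted with others at different times off drug. A separate SFU table would only partly help, because its visits are anchored to the withdrawal visit.
- Participants who start another disease-modifying therapy (DMT) or commercial ocrelizumab leave the study and drop out of the denominator without comment.
- Samples taken beyond SFU come from people selected for not having repleted.

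At stake is the description of how long B-cell depletion lasts. A reader could take a low late percentage as the share recovered by then.

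**Working it through.** **Plan's own figure.** The 72-week median is an observed Phase II result in 51 participants. It cannot be reproduced without patient-level data and is taken as given.

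**Inputs.** Median 72 weeks and range 27–175, n = 51 (Protocol 7.3.1.1); SFU of 48 weeks (Synopsis). The distribution shapes, the interval of the earlier monitoring and its exit rule are assumptions.

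**1. Share repleted by week 48 if the median is 72.**
- Exponential: 1 − 0.5^(48/72) = 37%.
- Exponential starting at week 27: 1 − 0.5^((48−27)/(72−27)) = 28%.
- Weibull, shape 1.5 to 3: 31% to 19%.
- Lognormal: log SD = ln(175/27) / expected range of 51 standard normals = 1.869/4.51 = 0.414, and F(48) = Φ(ln(48/72)/0.414) = 16%. Varying the SD by ±25% gives 10–22%.

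Across shapes this is about 10–37%, so 63–90% would be unrepleted when follow-up ends. If 50 patients were followed, the chance that at least half replete by week 48 is 4% (exponential) and below 0.1% (delayed exponential or lognormal with SD 0.414).

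**2. Selection in late monitoring.** Suppose participants leave sampling once repleted, and the denominator is those sampled at the visit. With monitoring interval d, the visit percentage at t is [F(t) − F(t−d)] / [1 − F(t−d)]. For the lognormal with median 72 and log SD 0.41, F(48) = 0.161, F(60) = 0.328, F(72) = 0.500, F(84) = 0.647 and F(96) = 0.759.

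| Week | True cumulative | d = 12 weeks | d = 24 weeks |
|---|---|---|---|
| 72 | 50% | (0.500−0.328)/0.672 = 26% | (0.500−0.161)/0.839 = 40% |
| 96 | 76% | (0.759−0.647)/0.353 = 32% | (0.759−0.500)/0.500 = 52% |

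For log SD 0.35–0.50 the week-72 ranges are 22–28% (d = 12) and 37–43% (d = 24). At week 96 they are 25–38% and 44–59%, against a cumulative 72–79%.

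**3. Time origin.** This step applies only if visits are counted from first infusion. At week 96, only those last infused at week 48 or week 72 are within 48 weeks of their last infusion. Their repleted shares (log SD 0.414) are F(48) = 16.4% and F(24) = 0.4%. The visit percentage then depends only on the mix of the two groups:
- 75:25 (mostly early stopping): 0.75×16.4 + 0.25×0.4 = 12%.
- 50:50 (even stopping): 8%.
- 37.5:62.5 (mostly late stopping): 6%.

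One identical recovery curve gives three answers. The stopping patterns are assumed.

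**The case against.** Several stronger readings are tempting, and the documents do not support them.

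- A reader might infer that the repletion percentage is counted from first infusion. SAP 4.6.5 uses that origin for the median-count plot; the repletion sentence names none, and SAP 4.6 also promises summaries for the SFU period. A first-infusion clock is a possible reading only. The mixing of on- and off-treatment data rests instead on SAP 4.6.8 and 4.6.9.
- A reader might infer that repletion is assessed over 48 weeks only. That describes current follow-up. The SAP still takes in earlier B-cell monitoring data, and the shortening was deliberate and explained.
- A reader might infer that the purpose of SFU cannot be met. Section 4.1.6.8 promises an evaluation of repletion, alongside safety and efficacy aims. It does not promise a median, and time to repletion is not a declared endpoint.
- A reader might infer that advice on live vaccines or other MS therapies hangs on this table. The protocol ties that advice to each participant's own B-cell status.
- A reader might infer that no time-to-repletion analysis exists anywhere. SAP 4.6.9 refers to a Global Safety Pooling SAP that is not available here, so the statement can be made only of this SAP.

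The fair counter-case is that this is one descriptive laboratory table. The selection bias in step 2 also disappears if repleted status is carried forward over a fixed denominator, which the wording permits. That stands as a condition on the size of the bias. It does not supply the missing origin, denominator or censoring rule.

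**Conclusion.** The point holds as a gap in a descriptive safety analysis. As written, the by-timepoint percentage does not estimate recovery after the last infusion. If its denominator is those sampled at each visit, late values come from a group selected for slow recovery and understate the cumulative figure. The illustrative size is 26–40% against 50% at week 72 and 32–52% against 76% at week 96. This rests on a lognormal shape with median 72 and log SD 0.41, exit at repletion, and a 12- or 24-week interval, none of which the documents fix.

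Separately, about 10–37% would replete within 48 weeks under the Phase II median. A median is therefore unlikely to be reached from current follow-up alone, whatever the method; the curve up to week 48 can still be estimated. Type I error, power and the primary and secondary efficacy conclusions are unaffected.

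**What to change.** For off-treatment data, add a Kaplan-Meier or interval-censored analysis of time from the last ocrelizumab infusion to repletion, using the existing SAP definition. Interval censoring suits sampling every 12 weeks or less often.

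- Use the SFU and earlier B-cell monitoring samples already collected.
- Censor at the last CD19 sample, death, start of another DMT or commercial ocrelizumab, or rollover, and show numbers at risk.
- Report the percentage repleted at 24 and 48 weeks. Give the median and later timepoints only if numbers at risk support them.
- State that the median may not be estimable from 48-week follow-up alone.
- Keep by-visit repletion percentages for on-treatment visits only.

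The cost is a paragraph of SAP text and one extra analysis. No longer follow-up and no linkage to the rollover study is needed; the documents say only that participants may complete the same follow-up period there.

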2.2 RATIONALE FOR THE STUDY AND BENEFIT–RISK ASSESSMENT

This study is a pivotal Phase III clinical trial, and is composed of the following periods: a double-blind, double-dummy, treatment period, a safety follow-up period, and an OLE phase. The double-blind, double-dummy, treatment period is designed to demonstrate the efficacy and safety of ocrelizumab in RMS in comparison with high-dose, high-frequency (HDHF) IFN (Rebif). The OLE phase serves to evaluate the long-term safety, tolerability, and efficacy of ocrelizumab treatment in participants with relapsing forms of MS.

This study is part of a broader, confirmatory clinical development program investigating the safety and efficacy of ocrelizumab in participants with both RMS and PPMS. An OLE phase of the Phase II Study WA21493/ACT4422G is ongoing for eligible participants with RRMS. There are 3 ongoing Phase III pivotal trials (including the one presented in this protocol), 2 trials in RMS and 1 trial in PPMS. Please see Section 4.1.6 for further details on study design and choice of comparator.

A benefit–risk assessment was conducted to determine whether there is any impact on the concomitant use of severe acute respiratory syndrome coronavirus 2 (SARS-CoV-2) vaccines on the conduct of this study. Based on this assessment, no impact is anticipated to affect the efficacy and safety in participants enrolled in ocrelizumab clinical trials. Existing information on identified risks, safety monitoring, and risk mitigation measures related to administration of vaccines (including those for SARS-CoV-2) provided in the study protocol (namely, immunization [Section 5.5.3], concomitant therapy [Section 5.5], and impaired response to vaccination [Section 7.3.1.1]) are considered adequate.

Data from the pivotal Phase III studies of ocrelizumab in RMS and PPMS show that preexisting humoral immunity to common viral and bacterial antigens is not affected by ocrelizumab treatment. The vaccination study (BN29739, VELOCE) showed that participants with MS treated with ocrelizumab were able to mount a humoral immune response to non-live vaccines and new antigens. The antibody immune response was considered protective, albeit with reduced levels of antibodies compared with controls. In this study, vaccines were given as early as 12 weeks after the first ocrelizumab

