4.1.6.7 Rationale for the Open-Label Extension Phase

Multiple sclerosis is a chronic disease that requires lifelong treatment to reduce the frequency of relapse and accumulation of disability. Once a participant is diagnosed with definite MS, accepted treatment guidelines propose that he/she be offered lifelong treatment because no evidence suggests that MS spontaneously remits (Rio et al. 2011).

Results of long-term, follow-up, exploratory studies suggest that exposure to DMT for more than 2 years improves outcomes by delaying the time to disability progression. Furthermore, accumulating evidence indicates that, in MS, inflammatory damage is a continuous process leading to demyelination and axonal transection and is the substrate of permanent disability in MS (Trapp et al. 1998; Lindberg et al. 2004; Freedman 2011).

Based on the long-term efficacy and safety data in Phase II Study WA21493/ACT4422G (for details, please see Section 2.1.4.1), it is justified to offer ocrelizumab to participants who would otherwise receive treatment that, in most cases, is modestly effective in reducing the frequency of relapses and in preventing sustained disability (Scalfari et al. 2010; Kappos et al. 2012).

Thus, participants who complete the 96-week, double-blind, double-dummy, treatment period will be offered the option to participate in an OLE phase of the study. Providing participants with the opportunity to prolong treatment with ocrelizumab beyond 2 years will provide more information on the long-term safety of ocrelizumab in RMS (e.g., the risk of infections/serious infections/opportunistic infections or potential loss of previously acquired immunity [e.g., hypogammaglobulinemia, specific serological titers]), as well as allow further collection of tolerability and efficacy information from participants with long-term exposure. Furthermore, the OLE phase will increase the overall number of participants exposed and participant-year exposure, thus increasing the likelihood of detecting rare events and the understanding of the safety/efficacy profile. Analyzing the long-term safety, tolerability, and efficacy of ocrelizumab is of critical importance to eventually help clinicians make informed decisions on therapy for participants (Day and Williams 2007).

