5.5.2.1 Prohibited Concomitant Treatments for MS

Therapies for MS noted in the exclusion criteria under “Exclusions Related to Medications” (Section 5.3) are not permitted during the double-blind, double-dummy, treatment period, the OLE phase screening period, or the OLE phase with the exception of systemic corticosteroids for the treatment of a relapse; IV Ig is also permitted. For participants who withdraw from treatment with ocrelizumab and enter safety follow-up, alternative treatments for MS judged clinically appropriate by the Treating Investigator are allowed. However, because sufficient data are not available to inform risks associated with switching to other products, the following recommendations are given:

- Caution is advised while participants remain B-cell depleted
- Because of the unknown safety risk of administering DMTs for MS after discontinuation of ocrelizumab, certain treatments for MS such as

lymphocyte-depleting agents or lymphocyte-trafficking blockers (e.g., alemtuzumab, natalizumab, fingolimod, dimethyl fumarate, cyclophosphamide, azathioprine, etc.) are **strongly discouraged** for as long as the participant remains B-cell depleted because of unknown effects on the immune system (e.g., increased risk, incidence, or severity of infection)

Participants who start treatment with commercial ocrelizumab *or another DMT* will discontinue participation in the study completely and will not enter or continue in the safety follow-up period.

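### The SAP's percentage with a positive antibody titre can partly hide patients who lose existing immunity; no output counts those losses

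*SAP*

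**What the plan says.** Protocol 4.1.6.7 justifies the open-label extension (OLE) partly by the need to learn about "potential loss of previously acquired immunity [e.g., hypogammaglobulinemia, specific serological titers". Protocol 5.11.1 says the titres serve to assess ocrelizumab's effect on specific humoral immunity.

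The titre paragraph of SAP 4.6.5 says that, if data are available, titres to the four antigens "will be summarized for number and percentages of patients with positive level". It adds that the mumps assay was changed and that results from both methods will be presented for the OLE.

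The same section opens with general rules: "All laboratory assessments will be summarized or listed when applicable", and "Absolute value and change from baseline values at each visit will be summarized". Where several results fall in one time window, "the worst value for that parameter will be presented in the summary table". For immunoglobulins the plan is more specific: "At each timepoint, the number and percentage of patients with immunoglobulin levels lower than the lower limit of normal will be presented".

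Protocol 5.5.2.1 restricts other MS therapies during treatment but states that "IV Ig is also permitted". Protocol 5.5.1 treats preventive vaccines received on study as concomitant medication. SAP 4.6.5 has no rule for titre or immunoglobulin values drawn after either.

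**The concern.** Loss of acquired immunity happens within a patient: a titre that was positive before ocrelizumab becomes negative. The specified output is a cross-sectional percentage at a visit, and it moves only by the difference between losses and gains. A steady percentage can mean that nobody changed, or that some patients lost a titre while others gained or regained one.

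Proportions of this kind already carry weight. Protocol 5.5.3 and 7.3.1.1 report that the proportion with positive titres after two years was similar to baseline, and Protocol 2.2 states that "preexisting humoral immunity to common viral and bacterial antigens is not affected by ocrelizumab treatment". Similar proportions do not by themselves establish that.

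The SAP uses baseline status for other safety data. Anti-drug antibodies get baseline prevalence, post-baseline incidence and treatment-induced cases (4.6.5), and the C-SSRS gets shift tables (4.6.2). Titres get neither. They are scheduled at baseline and Weeks 12, 24, 48, 72 and 96 (Protocol Table 1) and repeatedly in the OLE (Table 3), so the within-patient count is available.

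**Working it through.** The plan gives no figure to reproduce. The check is a reading of the sections above plus an illustration of what a net percentage can conceal.

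**Inputs.** n = 400 per arm (Protocol 4.2), all assumed to have paired samples. Baseline positivity p0 is not in the documents and is assumed to be 80%, 90% or 95%. Losses, gains and restorations are also assumptions.

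**Identity.** If a fraction L of baseline positives are negative at a visit and a fraction G of baseline negatives are positive, then p1 = p0(1 − L) + (1 − p0)G. Knowing p0 and p1 does not determine L.

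**Limits on the number lost.** The number of baseline positives now negative lies between max(0, n(p0 − p1)) and min(n·p0, n(1 − p1)).

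| p0 | Percentage unchanged | Upper limit as share of baseline positives | Net fall of 2 points |
|---|---|---|---|
| 80% | 0 to 80 | 80/320 = 25.0% | 8 to 88 |
| 90% | 0 to 40 | 40/360 = 11.1% | 8 to 48 |
| 95% | 0 to 20 | 20/380 = 5.3% | 8 to 28 |

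Each upper limit in the unchanged column requires every baseline negative to turn positive, so these are logical limits, not forecasts.

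**Gain needed for complete masking.** Setting p1 = p0 gives G = p0·L/(1 − p0).

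- p0 = 80%: L of 5% to 10% needs G of 0.80 × 0.05/0.20 = 20% to 40%.
- p0 = 90%: 0.90 × 0.05/0.10 = 45%, up to 90%.
- p0 = 95%: 0.95 × 0.05/0.05 = 95% for a 5% loss; impossible for 10%.

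**Partial masking at p0 = 90%** (360 positive, 40 negative):

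- 8% lose (28.8), nothing restored or gained: (360 − 28.8)/400 = 82.8%. The loss shows.
- 8% lose, half of those restored by the visit (14.4): 345.6/400 = 86.4%.
- As above, and 36% of negatives gain (14.4): 360/400 = 90.0%. The loss disappears.
- 5% lose (18), a quarter restored (4.5), 20% of negatives gain (8): 354.5/400 = 88.6%. The table shows a net fall of 5.5 patients; 18 lost a titre at some point.

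**Do the general rules close the gap?** If they reach titres, a mean change from baseline still does not say how many patients crossed from positive to negative, and a listing is not a count. The worst-value rule acts within one time window, so it does not retain a loss reversed at a later visit. The CD19 and immunoglobulin paragraphs each repeat change from baseline; the titre paragraph does not, which leaves the reach of the general rules unclear.

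**The case against.** A reader might infer that the percentage positive is the only titre output and that individual loss cannot be seen. The documents do not support that. The general rules of SAP 4.6.5 may bring in absolute values, change from baseline and listings, and paired samples exist. What is missing is a planned count.

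A reader might also infer that values restored by IV immunoglobulin or vaccination are deliberately counted as positive or normal. No text says so; it follows only from silence. Vaccination is also a narrow route. Protocol 5.5.3 advises against live vaccines, naming mumps and rubella, during treatment and while B cells are depleted, so it concerns mainly S. pneumoniae. IV immunoglobulin could affect all four titres and IgG, but the number who received it is not given. For immunoglobulins, a fall is counted at the visit where it occurs; only later visits could be altered.

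Full masking at high baseline positivity needs implausibly large gains, as the working shows. To hide a between-arm difference in the double-blind period, gains or restorations would also have to be larger on ocrelizumab than on interferon. This limits the point to partial masking, most relevant in the OLE, where there is no concurrent control.

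The mumps assay change is disclosed and both methods are to be shown. What is not stated is which assay is compared with baseline.

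Removing values after IV immunoglobulin from the main table would discard later data from the patients with the lowest IgG. That is a good reason to confine the exclusion to a sensitivity table.

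Finally, SAP 4.6.9 refers to a separate Global Safety Pooling SAP that cannot be checked here, so the gap is shown for this SAP only. None of these objections removes the case for a loss count.

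**Conclusion.** The point holds in limited form. The titre-specific output is a net percentage, which can partly hide within-patient loss of positivity, and nothing else in this SAP counts that loss although the protocol names it as a safety question. The size is unknown. In the illustration with 90% positive at baseline, 18 patients with a loss appear as a net fall of 5.5; with few gains or restorations, an 8% loss would show as a drop to 82.8%. These figures rest on assumed baseline positivity, assumed loss and gain rates, and complete pairing of 400 patients.

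It would go too far to conclude that immunity was lost, or that the protocol's statement about preserved immunity is wrong; the percentages alone cannot settle either. No efficacy conclusion is affected. The addition is worth making before the final CSR, which SAP 2.4 still lists as planned.

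**What to change.** Add to the titre paragraph of SAP 4.6.5:

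- For each antigen, among patients positive at their last sample before ocrelizumab (at baseline in the interferon arm), report the number and percentage who become negative, at any time and confirmed at the next sample. A baseline-by-visit shift table would also serve.
- For the double-blind period, present this by arm with a 95% CI for the difference. For the OLE, present it descriptively from the first ocrelizumab dose.
- Keep the percentages positive already planned.
- Keep all values in the main table. Flag titre and immunoglobulin values after IV immunoglobulin, and S. pneumoniae titres after pneumococcal vaccination, and give a sensitivity table that sets them aside.
- For mumps, compare with baseline only within the same assay.

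The cost is SAP wording and a few tables; no new data are needed. Denominators shrink to initially positive patients (320 to 380 of 400 at 80% to 95% positivity), and patients without a same-assay mumps baseline drop out of that comparison. The double-blind comparison would be post hoc, because the primary CSR is complete, and should be labelled so.
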